### **Objectives Endpoints** To determine the benefit of relugolix 40 mg Proportion of patients who are better or much once daily co-administered with 24 weeks of better on the PGIC for dyspareunia at low-dose estradiol and norethindrone acetate Week 24/EOT. compared with placebo on the PGIC for dyspareunia. Change from Baseline to Week 24/EOT in the To determine the benefit of relugolix 40 mg mean dyspareunia functional impairment on once daily co-administered with 24 weeks of the sB&B scale. low-dose estradiol and norethindrone acetate compared with placebo on effects on dyspareunia-related functional effects (Subject Modified Biberoglu and Behrman [sB&B]). To determine the benefit of relugolix 40 mg Change from Baseline to Week 24/EOT in the once daily co-administered with 24 weeks of severity scores on the PGA for pain. low-dose estradiol and norethindrone acetate compared with placebo on the Patient Global Assessment (PGA) for pain. To determine the benefit of relugolix 40 mg Proportion of responders at Week 24/EOT once daily co-administered with 24 weeks of based on EHP-30 Pain Domain scores; low-dose estradiol and norethindrone acetate compared with placebo on function measured by the Endometriosis Health Profile (EHP)-30 Pain Domain. To determine the benefit of relugolix 40 mg Change from Baseline to Week 24/EOT in the once daily co-administered with 24 weeks of function impairment on the PGA for function. low-dose estradiol and norethindrone acetate compared with placebo on the PGA for function. To determine the benefit of relugolix 40 mg Change from Baseline to Week 24/EOT in once daily co-administered with 24 weeks of each of the non-pain EHP-30 domains low-dose estradiol and norethindrone acetate (Control and Powerlessness, Social Support, compared with placebo on endometriosis-Emotional Well-Being, and Self-Image). associated quality of life (Control and Powerlessness, Social Support, Emotional Well-Being, and Self-Image domains of the EHP-30). To determine the benefit of relugolix 40 mg Change from Baseline to Week 24/EOT in the once daily co-administered with 24 weeks of mean dysmenorrhea functional impairment on low-dose estradiol and norethindrone acetate the sB&B scale. compared with placebo on dysmenorrhearelated functional effects (sB&B). To determine the benefit of relugolix 40 mg Change from Baseline to Week 24/EOT in the once daily co-administered with 24 weeks of mean NMPP functional impairment on the low-dose estradiol and norethindrone acetate sB&B scale. compared with placebo on NMPP-related functional effects (sB&B).

#### **Objectives Endpoints** The secondary efficacy objectives and endpoints below are based on comparisons between Group B and Group C: To determine the benefit of relugolix 40 mg Proportion of responders at the Week 24/EOT once daily for 12 weeks followed by 12 weeks pain assessment period, based on their of relugolix 40 mg once daily co-administered dysmenorrhea NRS scores recorded in a daily with low-dose estradiol and norethindrone eDiary. acetate compared with placebo on dysmenorrhea measured by the NRS. Proportion of responders at the Week 24/EOT To determine the benefit of relugolix 40 mg once daily for 12 weeks followed by 12 weeks pain assessment period, based on their NMPP NRS scores recorded in a daily eDiary. of relugolix 40 mg once daily co-administered with low-dose estradiol and norethindrone acetate compared with placebo on NMPP measured by the NRS. To determine the benefit of relugolix 40 mg Change from Baseline at Week 24/EOT in the EHP-30 Pain Domain scores. once daily for 12 weeks followed by 12 weeks of relugolix 40 mg once daily co-administered Proportion of responders at Week 24/EOT based on EHP-30 Pain Domain scores. with low-dose estradiol and norethindrone acetate compared with placebo on function measured by the EHP-30 Pain Domain. Safety To determine the safety of 24 weeks of Treatment-emergent adverse events, change relugolix 40 mg once daily co-administered in vital signs (including weight), clinical with either 12 or 24 weeks of low-dose laboratory tests, and electrocardiograms estradiol and norethindrone acetate. (ECGs). Percent change from Baseline to Week 12 in To determine the percent change from Baseline to Week 12 in bone mineral density bone mineral density at the lumbar spine at the lumbar spine (L1-L4) in Group A (L1-L4) in Group A compared with Group B compared with Group B. as assessed by dual-energy x-ray absorptiometry (DXA). To determine the change in bone mineral Percent change from Baseline to Week 24 in density after 24 weeks of treatment with bone mineral density at the lumbar spine (L1-L4), femoral neck, and total hip as relugolix 40 mg once daily co-administered with either 12 or 24 weeks of low-dose assessed by DXA. estradiol and norethindrone acetate. To determine the incidence of vasomotor Incidence of vasomotor symptoms. symptoms with relugolix 40 mg once daily coadministered with either 12 or 24 weeks of low-dose estradiol and norethindrone acetate. Pharmacodynamic To evaluate the pharmacodynamic effects of Changes from Baseline to Week 24 in pre-24 weeks of relugolix 40 mg once daily when dose concentrations of LH, FSH, estradiol, co-administered with low-dose estradiol and and progesterone. norethindrone acetate.

Objectives		Endpoints	
	Explor	ratory	
	To determine the benefit of relugolix 40 mg once daily co-administered with either 12 or 24 weeks of low-dose estradiol and norethindrone acetate on patient-reported quality of life outcomes related to endometriosis as follows:		
	
 
Endometriosis-associated quality of life (EHP-30 total score).
 
	• Change from Baseline to Week 24/EOT in the EHP-30 scale total score.	
	
 
Effects of endometriosis on work (EHP Work Domain).
 
	• Change from Baseline to Week 24/EOT in the EHP Work Domain score.	
	
 
Quality of life as assessed by the European Quality of Life Five-Domain Five-Level (EQ-5D-5L) scale.
 
	• Change from Baseline to Week 24/EOT in the EQ-5D-5L scale score.	

# 4. INVESTIGATIONAL PLAN

# 4.1. Overall Study Design

The SPIRIT 2 study is an international phase 3 randomized, double-blind, placebo-controlled efficacy and safety study to evaluate oral relugolix 40 mg once daily co-administered with either 12 or 24 weeks of low-dose estradiol (1.0 mg) and norethindrone acetate (0.5 mg) compared with placebo. Approximately 600 women with endometriosis-associated pain will be enrolled and randomized 1:1:1 to the relugolix plus low-dose hormonal add-back therapy group (Group A,  $N \approx 200$ ), the relugolix monotherapy followed by co-administration with low-dose hormonal add-back therapy group (Group B,  $N \approx 200$ ), or the placebo group (Group C,  $N \approx 200$ ). Stratification variables will include: geographic region (North America versus Rest of World) and years since surgical endometriosis diagnosis (< 5 or  $\geq$  5 years).

Eligible patients will have endometriosis that has been visualized directly or during surgery and/or documented by histopathology within 10 years of the Screening visit. Additionally, patients will have no history of chronic pelvic pain other than that caused by endometriosis and will not be using opioid analgesics or frequent non-opioid analgesics for chronic pain or recurring pain other than that due endometriosis. Patients receiving hormonal contraceptives will discontinue these 28 to 56 days prior to the start of the single-blind Run-In Period. At the Screening visit, patients will answer questions as to the severity of their dysmenorrhea and NMPP. Only those whose pain is self-characterized as moderate, severe, or very severe for both dysmenorrhea and NMPP will proceed to additional Screening visit procedures and Run-In procedures. Patients who are not excluded by the results available at the end of the Screening visit will be dispensed an eDiary and will begin a 35-day Run-In Period on the next day. During the single-blind Run-In Period, in which only patients will be blinded, the patients will take one placebo tablet and one placebo capsule each day and report their pain and analgesic medication use daily in the eDiary. Only study-specific analgesic medications should be used starting with

the second day of the Screening visit (if the Screening visit is conducted over more than one day), during the Run-In Period, and subsequently. These medications will be taken for control of pain and not prophylactically. Final eligibility will be based on severity of pain determined by the specified NRS scores for dysmenorrhea and NMPP and PGIC for NMPP obtained during the Run-In Period as defined in the inclusion and exclusion criteria. For patients with fewer than 3 dysmenorrhea scores during R1 through R35, Run-In will be continued through up to Day R70, with the Sponsor/designee approval (see Section 6.2, until the 3 dysmenorrhea scores are obtained and these 3 scores will be used to determine eligibility for dysmenorrhea. If needed, Run-In may also be extended for logistical reasons (eg, need for repeat endometrial biopsy) by an additional up to 35 days (ie, through Run-In Day R70) with Sponsor/designee approval.

Run-In Day R1 is defined as the day that the first dose of single-blind study drug is taken. Once eligibility has been confirmed, patients will be randomized on Baseline Day 1 and will begin double-blinded study drug treatment on the same day. The Run-In Period through the day prior to the first dose of randomized study drug will serve as the Baseline pain assessment period for the study. During the Randomized Treatment Period, study participants will take double-blinded study treatment (1 tablet and 1 capsule) orally once daily for 24 weeks. The last dose of study drug will be taken on the day prior to the Week 24 visit.

Between the Baseline Day 1 and Week 24 visits, patients will attend visits every 4 weeks. During the Run-In Period and at the Week 12 and Week 24 visits, each patient will have an assessment of bone mineral density with DXA. Patients will complete a daily eDiary from the day prior to Run-In Day 1 through the Follow-Up visit to record study drug treatment, assessment of pain using the NRS, menstrual bleeding and its severity, analgesic use, and the functional effects of endometriosis-associated pain (sB&B). Evaluation of function (EHP-30), quality of life questionnaires, PGICs, and PGAs for pain will be completed during the visits in an electronic tablet and a PGA for function will be completed as specified in the Schedule of Activities. Patients will continue use of protocol-specified rescue analgesic medications, as needed, until the end of the Follow-Up Period.

Safety will be assessed throughout the study by the monitoring of adverse events, vital signs and weight, physical examinations including visual acuity, clinical laboratory tests, 12-lead ECGs, and bone mineral density by DXA. Pharmacodynamics samples will be collected for assessment of LH, FSH, estradiol, and progesterone at intervals during the study. Eligible patients, including women randomized to placebo, will be offered the opportunity to enroll in a 28-week open-label extension study where patients will receive relugolix co-administered with low-dose estradiol and norethindrone acetate. Patients who do not enroll into the extension study will have a Follow-Up visit approximately 30 days after the patient's last dose of study drug.

Patients who are not proceeding to the extension study and who have bone mineral density loss of > 2% at the lumbar spine (L1-L4) or total hip relative to the Baseline measurement at their Week 24/Early Termination visit or most recent study scan will undergo further testing and follow-up to evaluate recovery (see Section 6.8 for details). Patients whose menses has not resumed as of the Follow-Up visit for unexplained reasons (eg, not explained by concomitant medications or medical procedures) will be contacted by telephone to determine if menses has resumed (see Section 6.8 for details). Patients with reductions in visual acuity will be referred for ophthalmology consultation (see Section 6.8 for details).

Figure 4-1 MVT-601-3102 Study Schematic

[figure not shown]
[figure not shown]

Figure 4-2 Schematic of MVT-601-3102 Screening and Run-In Procedures for Determining Eligibility Based on Pain Scores

# **4.2.** Discussion of Study Design, Including Dosing Rationale and Choice of Control Group

This phase 3 study is one of two replicate studies designed to establish the efficacy and safety of relugolix 40 mg once daily in women with endometriosis-associated pain. This study will focus on the primary objective of demonstrating a reduction in dysmenorrhea and NMPP, the two most common symptoms that lead to diagnosis of endometriosis. The study is designed to demonstrate the benefit and safety of relugolix 40 mg once daily co-administered with low-dose estradiol (1.0 mg) and norethindrone acetate (0.5 mg) for 24 weeks. An additional relugolix arm dosed with 12 weeks of relugolix monotherapy 40 mg once daily followed by 12 weeks of relugolix 40 mg once daily co-administered with low-dose estradiol and norethindrone acetate will be used to provide an assessment of the requirement for the low-dose hormonal add-back therapy to mitigate the adverse effects of relugolix monotherapy on bone mineral density loss and vasomotor symptoms. An open-label extension study (MVT-601-3103) is planned to provide additional safety and efficacy data through a total of up to 52 weeks.

This study is randomized, double-blind, and placebo-controlled. Patients who meet the threshold levels of NRS worst pain scores for dysmenorrhea and NMPP during a single-blind placebo Run-In Period will receive double-blind treatment for 24 weeks. The purpose of the single-blind Run-In Period is to decrease from the randomized study population who exhibit a robust placebo response or sufficient placebo response that they do not meet the minimum threshold for pain severity. Rescue analgesic medications are specified by the protocol and no other analgesics will be allowed. Starting with the second day of the Screening visit, patients will take study-specified rescue analgesic medications as needed (but not prophylactically). Patients will report their pain scores and analgesic medication usage daily in an eDiary on instruments that have undergone validation and cognitive debriefing in women with endometriosis. Appropriately selected secondary endpoints aimed at evaluation of functional effects of endometriosis, dyspareunia, and quality of life related to endometriosis-associated pain are designed to further describe the clinical benefit of treatment.

The studies have two co-primary endpoints that separately evaluate the proportion of responders for dysmenorrhea and NMPP. The requirement to show efficacy on each endpoint is a more stringent requirement than a single primary endpoint because both of these important aspects of endometriosis-associated pain will need to be significantly improved by the treatment for the study to have met its primary objective. The level of pain severity reduction that constitutes a responder will be based on a clinically significant reduction determined by the patient-reported global assessments within the study. Use of analgesics is incorporated within the response definition.

Patients will visit the study site approximately every 4 weeks for safety evaluations, which include bone mineral density measurements, centrally-read ECGs, clinical laboratory assessments that include lipid measurements, visual acuity testing, physical examination, and vital signs. The study eligibility criteria have been designed to minimize risk to patients and rules for evaluation of liver test abnormalities, consistent with US Food and Drug Administration (FDA) guidance, have been incorporated into the protocol. A 28-week open-label extension study will be offered to all eligible women completing the 24-week phase 3 studies; this will provide a total of up to 52 weeks of safety and efficacy data in the women originally randomized to active therapy.

### The study has three groups:

• Group A: relugolix 40 mg orally once daily co-administered with over-encapsulated estradiol (1.0 mg) and norethindrone acetate (0.5 mg) once daily, referred to as estradiol/norethindrone acetate for 24 weeks;

- Group B: relugolix 40 mg orally once daily for 12 weeks, followed by relugolix 40 mg orally once daily for another 12 weeks co-administered with estradiol/norethindrone acetate; and
- Group C: relugolix placebo tablet and an estradiol/norethindrone acetate placebo capsule once daily for 24 weeks.

The dose of relugolix was selected for the study (40 mg once daily) to maximally suppress estradiol levels in women with endometriosis-associated pain so that all women start from a stable floor of very low estrogen. Estradiol/norethindrone acetate will be co-administered to add-back, in a controlled fashion, a dose of estradiol known to prevent bone mineral density loss in the majority of women and to mitigate other tolerability adverse effects such as vasomotor symptoms. To ensure blinding, an over-encapsulated fixed-dose combination tablet of estradiol/norethindrone acetate will be co-administered with relugolix once daily.

Treatment Group A has been selected to provide the maximal benefit/risk ratio to women by providing relugolix 40 mg once daily, the dose known to maximally suppress estradiol levels and to provide the greatest decrease in endometriosis-associated pain, co-administered with low-dose estradiol/norethindrone acetate add-back therapy, to protect against bone mineral density loss and improve tolerability. Treatment Group B is intended to assess the requirement for low-dose hormonal add-back therapy to mitigate the adverse effects of relugolix monotherapy on bone mineral density loss and vasomotor symptoms. Placebo has been selected as the comparator because it facilitates double-blinding and allows for a clearer characterization of the safety and efficacy profile of relugolix, a new chemical entity, than would be possible with an active comparator. Furthermore, there is no single standard-of-care treatment for endometriosis-associated pain.

The selection of the proposed active treatment arm is supported by the following evidence-based reasons:

- Relugolix 40 mg once daily suppressed serum estradiol to less than postmenopausal levels, and significantly reduced endometriosis-associated pain in a well-designed large dose-finding phase 2 study.
- Low-dose hormonal add-back therapy has been demonstrated in combination with GnRH
  agonists and antagonists to attenuate loss in bone mineral density and the frequency of
  vasomotor symptoms such as hot flushes resulting from a hypoestrogenic state. This
  low-dose estradiol/norethindrone acetate therapy is currently approved for use in
  postmenopausal women to prevent osteoporosis and moderate to severe vasomotor
  symptoms.
- Because the bone is exquisitely sensitive to estrogen, particularly as compared with the
  doses of estrogen required to reverse the effects of relugolix on endometriosis-associated
  pain, the low doses of estradiol/norethindrone acetate that protect against bone mineral
  density loss are not expected to significantly impact the ability of relugolix to reduce
  endometriosis-associated pain.

# 4.3. Selection of Study Population

The study population will include approximately 600 premenopausal women aged 18 to 50 years with endometriosis-associated pain.

Deviations from inclusion and exclusion criteria are not allowed because they can potentially jeopardize the scientific integrity of the study, regulatory acceptability, or patient safety. Therefore, adherence to the criteria as specified in the protocol is essential. Any questions regarding patient eligibility and entry criteria should be discussed with the medical monitor.

# 4.3.1. Inclusion/Exclusion Criteria

Inclusion Criteria (all inclusion criteria must have been met prior to randomization):

- 1. Has voluntarily signed and dated the informed consent form prior to initiation of any screening or study-specific procedures;
- 2. Is a premenopausal female aged 18 to 50 years old (inclusive) on the day of signing date of the informed consent form;
- 3. By the patient's report, had 2 consecutive regular menstrual cycles (ie, 21 to 35 days in duration) immediately prior to randomization. For patients who have washed off hormonal contraceptives, the 2 regular cycles must be after the first (withdrawal) bleeding following discontinuation of contraceptives;
- 4. Has agreed to use only study-specified analgesic medications during the study and is not known to be intolerant to these;
- 5. Has a diagnosis of endometriosis and has had, within 10 years prior to signing the informed consent form, surgical or direct visualization and/or histopathologic confirmation of endometriosis, for example, during a laparoscopy or laparotomy;
- 6. During the Screening visit, the patient reports moderate, severe, or very severe pain during the most recent menses and for NMPP in the prior month;
- 7. During the Run-In Period Days R1 through R35, has at least 24 days of completed eDiary scores;
- 8. During the Run-In Period Days R1 through R35, has a dysmenorrhea NRS score ≥ 4.0 on at least 2 days AND
  - a. Mean NMPP NRS score  $\geq 2.5$ , OR
  - b. Mean NMPP NRS score ≥ 1.25 AND NMPP NRS score ≥ 5.0 on ≥ 4 days; For patients with fewer than 3 dysmenorrhea scores during Days R1 - R35, dysmenorrhea scores from Days R36 – 70 will be included in the eligibility determination until a total of 3 dysmenorrhea scores from the Run-In Period are available.
- 9. Has menstruated for at least 3 days during the Run-In Period;
- 10. Is not expected to undergo gynecological surgery or other surgical procedures for treatment of endometriosis (including ablation, shaving, or excision) during the study, including during the Follow-Up Period, and the patient does not desire such treatment during this time frame;

11. Has a negative urine pregnancy test at the Screening visit and on the Baseline Day 1 visit;

- 12. Agrees to use contraception during the study and for 30 days following the last dose of study drug. Specifically, agrees to use nonhormonal contraception as described in Section 4.7 consistently during the Screening Period, Run-In Period, and the Randomized Treatment Period and for 30 days following treatment discontinuation. However, the patient is not required to use the specified nonhormonal contraception if she:
  - a. Has a sexual partner(s) who was vasectomized at least 6 months prior to the Screening Period;
  - b. Had a bilateral tubal occlusion (including ligation and blockage methods such as EssureTM), at least 6 months prior to the Screening visit (patients with Essure must have prior confirmation of tubal occlusion by hysterosalpingogram and no evidence of "post-Essure syndrome" in the investigator's opinion);
  - c. Is not sexually active with men; periodic sexual relationship(s) with men requires the use of nonhormonal contraception as noted above; or
  - d. Practices total abstinence from sexual intercourse as her preferred lifestyle. Periodic abstinence is not acceptable;
- 13. Has an adequate endometrial (aspiration) biopsy performed during the Screening visit or Run-In Period or one that was locally performed within 6 months prior to Screening with results showing no clinically significant endometrial pathology (hyperplasia, polyp, or endometrial cancer).
  - Note 1: Patients for whom polyps are detected on the biopsy but are either not evident on ultrasound or < 2.0 cm by ultrasound are eligible.
  - Note 2: endometrial biopsies that were performed or repeated during the Run-In Period and meet criteria are acceptable;
- 14. If  $\geq$  39 years of age at the time of the Screening visit, has a normal mammogram (Breast Imaging Reporting and Data System category 1 to 2 or equivalent; see Appendix 1) during the Run-In Period or within 6 months prior to the Run-In Period.

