#### 9.3.1. Co-primary Efficacy Endpoints

The study has two co-primary efficacy endpoints comparing Group A versus Group C:

- Proportion of responders at Week 24/End of Treatment (EOT) pain assessment period, based on the dysmenorrhea NRS scores recorded in a daily electronic diary and use of rescue analgesics; and
- Proportion of responders at Week 24/EOT pain assessment period based on the NMPP NRS scores as recorded in a daily electronic diary and use of rescue analysesics.

A responder at Week 24/EOT is defined as a patient who had a reduction from Baseline of the determined threshold (or clinically meaningful difference) or greater from Baseline in pain and who did not have an increase in the use of rescue analgesic medications for endometriosis-associated pain during the Week 24/EOT pain assessment period compared with the use in the Baseline pain assessment period.

The Baseline pain assessment period is defined as the period from the date of the first dose of placebo in the Run-In Period through the day prior to the date of the first dose of randomized

Effective: 12-MAR-2018

study drug treatment The Week 24/EOT pain assessment period is defined as the last 35 calendar days immediately prior to and including the last dose of randomized study drug treatment.

Pain data collected in the Baseline pain assessment period will be used as baseline. The Baseline value for dysmenorrhea is defined as the mean NRS scores over the days with menses during the Baseline pain assessment period. The Baseline value for NMPP is defined as the mean NRS scores over the days without menses during the Baseline pain assessment period. The Baseline value for total dose counts is defined as the mean daily dose counts taken during the Baseline pain assessment period multiplied by 35.

The clinically meaningful difference will be determined for NMPP and dysmenorrhea separately (see the Statistical Analysis Plan for details). The anchor-based methods (using PGA for dysmenorrhea and PGA for NMPP as anchors) supplemented with both cumulative distribution function (CDF) and probability density function (PDF) curves will be considered as primary methods to derive the meaningful pain reduction thresholds to be used to define a responder.

Determination of the meaningful pain reduction threshold using PGIC as the anchor will also be explored as supportive.

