#### 9.3.1.3. Sample Size Justification

The following assumptions are used to determine the sample size for this study:

- 2-sided type I error rate: 0.05;
- Randomization: 1:1:1;
- Responder rate for Group C: 30-35%;
- Difference in responder rates between Group A and Group C: 20%;
- Dropout rate: 20%.

Assuming a dropout rate of 20%, approximately 200 women in relugolix Group A and 200 women in placebo Group C will provide at least 95% power at a 2-sided 0.05 significance level to detect a 20% difference in responder rates between Group A and Group C for each individual co-primary endpoint. This will provide an overall power of at least 90% for the study to detect a 20% treatment difference for both co-primary endpoints simultaneously. The responder rate for Group C is assumed to be between 30 and 35%. The proposed fixed sample size of 400 patients in Groups A and C is adequate to detect the target difference of 20% in responder rates between the two groups. It is calculated considering overall responder rates of close to 50% from which the maximum sample size is reached. With an additional 200 women in relugolix Group B, the total sample size will be approximately 600 women.

The assumed responder rate of 30 to 35% for Group C is within the range of responder rates (approximately 25 to 40%) observed in similar phase 3 endometriosis trials [Taylor, 2017]. The sample size and power calculations are based on the chi-squared test and were performed using the software package *nQuery* 4.0.0.0 (Statistical Solutions Ltd.).

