## 9 Form: AlarmSetup

Screen 1

MY80005-eDiary

23May2017

diary.

First the use of these actions are

Exit

Back

explained visually. Then you will practice using them by yourself.

Use the buttons below to move through the Training. Tap 'Next' to continue.

[figure not shown]

MY80005-eDiary

23May2017

Next >

Message 1

Screen 2 Screen 3 Message 3

Page 21 of 24

Version 3 MY80005-eDiary US English Screen Report 23May2017 Good! A list can be scrolled by placing a Now practice using the scrollable list. Scroll the list and tap '9 days ago'. finger on the list and by swiping the list upward until the needed list item is displayed. Avoid moving your finger on the screen when making a selection. Select first 1 Yesterday Please select first the list item '9 days ago', and tap 2 days ago then the 'Next' button. 3 days ago If you would like to go 4 days ago through the guide pages for the finger scrollable list 5 days ago again, use the 'Back' button 6 days ago to navigate back. 7 days ago Tap 'Next' to continue Tap 'Next' to continue Next > Back Next > Back Screen 4 Screen 5 Message 4 Text can be entered by tapping the text If a mistake is made during typing, box on the screen and then by typing with the displayed keyboard. The characters can be removed by selecting the delete button marked with a 'cross'. If the scrollable list does not scroll when you swipe it, it is not broken. The scrollable list can only be scrolled if there keyboard can be closed by tapping the green tick mark. is more content on the list than can fit on to the screen. X 123 Numbers can be typed by tapping the `123' button. Tap 'Next' to continue Tap 'Next' to continue Tap 'Next' to continue Next Back Next Next Screen 6 Screen 7 Screen 8

Page 22 of 24

Version 3

MY80005-eDiary

US English Screen Report 23May2017 Now practice typing text. Tap the text box below and type something, for example **`medicine 10'**. Did you take your dose of study treatment (tablet) **today**? (Example text) Info 1 Yes Please answer the required question(s) Tap 'Next' to continue Back Next > Back Next > Screen 9 Screen 10 Message 5 How would you rate your worst pelvic pain in the past 24 hours? Thank you! Pelvic pain is defined as localized pain in the lower part of the stomach, below the belly button. Thank you, your training is now complete. 0 1 2 3 4 5 6 7 8 9 10 Back Next > Screen 11 Note: Screen will show latteraly on device Tap 'Next' to continue to your eDiary. Back Next

Page 23 of 24

Screen 12

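### Do the low Run-In pain floors leave some women unable to meet the co-primary response threshold even with complete relief?

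*Protocol*

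**What the plan says.** Inclusion criterion 8 in Section 4.3.1 sets the pain floors. For menstrual pain the woman "has a dysmenorrhea NRS score ≥ 4.0 on at least 2 days AND" one of two nonmenstrual conditions: a mean NMPP score of at least 2.5, or "Mean NMPP NRS score ≥ 1.25 AND NMPP NRS score ≥ 5.0 on ≥ 4 days". Two neighbouring criteria bear on how low a mean can be: she "Has menstruated for at least 3 days during the Run-In Period", and over Days R1 to R35 she "has at least 24 days of completed eDiary scores".

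Section 9.3.1 defines a responder as "a patient who had a reduction from Baseline of the determined threshold (or clinically meaningful difference) or greater from Baseline in pain", provided rescue analgesic use has not risen. On the starting value, "The Baseline value for NMPP is defined as the mean NRS scores over the days without menses during the Baseline pain assessment period"; dysmenorrhea uses menses days in the same way. The period runs to the day before the first randomized dose, so it can extend beyond R35. The daily item is scored "0 1 2 3 4 5 6 7 8 9 10" (Appendix 2).

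The threshold is set separately for each pain measure from Patient Global Assessment anchors. Section 4.2 says that these come from within the study, Section 9.3.1 sends the reader to the SAP for details, and Section 9 has the SAP final before unblinding. No value is given, and the text does not say whether the threshold is in NRS points or percent.

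Section 9.3.1.3 sizes the trial "to detect a 20% difference in responder rates between Group A and Group C for each individual co-primary endpoint".

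**The concern.** The entry rule and the response rule look as if they were written without reference to each other. Criterion 8b is meant for women whose pain is severe but intermittent; their pain-free days pull the mean down. If response is then judged by a fixed number of points off that mean, some of these women start below the required drop. A woman with a Baseline mean of 1.25 cannot improve by 1.5 points. She would count as a treatment failure even if relugolix abolished her pain.

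Dysmenorrhea has the same gap, because the criterion counts days at 4 or more and says nothing about the mean. Both co-primary endpoints must succeed and the sample size has little slack, so even a modest share of certain non-responders could matter.

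**Working it through.** **Inputs.** Entry floors from Section 4.3.1; Baseline definition from Section 9.3.1; two-sided alpha 0.05, control rate 30-35%, difference 20 points, dropout 20%, about 200 per arm and the chi-squared test from Section 9.3.1.3.

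**Plan's own figure.** Evaluable per arm: 200 × (1 − 0.20) = 160. Power = Φ{[Δ√n − 1.96√(2p̄(1−p̄))] / √(p₁(1−p₁) + p₂(1−p₂))}.
- 30% vs 50%: [0.20 × 12.649 − 1.96 × √0.48] / √0.46 = 1.172 / 0.678 = 1.728, giving 95.8%.
- 35% vs 55%: [2.530 − 1.96 × √0.495] / √0.475 = 1.151 / 0.689 = 1.670, giving 95.3%.
- Both endpoints: 91.8% and 90.7% as products, or 91.6% and 90.5% as the lower bound 2p − 1.

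The claims of at least 95% per endpoint and at least 90% jointly hold.

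**How low can Baseline be?**
- NMPP: four days at 5 and twelve at 0 give 20/16 = 1.25. A score total of 35 over 28 nonmenstrual days also gives 1.25; seven further pain-free days before dosing make it 35/35 = 1.00.
- Dysmenorrhea, two days at 4 and the rest 0: 8/3 = 2.67 with three menses days, 8/5 = 1.60 with five, 8/7 = 1.14 with seven.

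**Drop needed under an assumed absolute threshold T.** Required percent reduction = 100 × T / Baseline.

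| T (points) | Baseline 1.25 | Baseline 2.5 |
|---|---|---|
| 1.0 | 80% | 40% |
| 1.25 | 100% | 50% |
| 1.5 | 120%, impossible | 60% |
| 2.5 | 200%, impossible | 100% |

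A threshold stated as a percent reduction would be attainable from any Baseline above zero.

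**Illustrative power.** Assume a share f of each arm cannot respond and the 20 points hold in the rest, so that both rates are multiplied by 1 − f, at 160 per arm.

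| f | Difference (points) | Power, control 30% / 35% |
|---|---|---|
| 0 | 20 | 95.8% / 95.3% |
| 5% | 19 | 94.2% / 93.4% |
| 10% | 18 | 92.2% / 91.0% |
| 20% | 16 | 87.0% / 85.0% |

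**What the Protocol does not supply.** T and f are both assumed. One argument for a large T is that ten NRS points over four PGA steps is 2.5 points per step. That maps an ordinal four-week rating (Appendix 3) evenly onto a mean of daily worst-pain scores that includes days scored 0. Averaging over low-pain days compresses the mean, so a PGA step may correspond to much less than 2.5. Nor would T = 2.5 bar every woman admitted through 8b: a mean of 2.4 over 28 days followed by seven days at 4 gives (67.2 + 28)/35 = 2.72.

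**The case for a change.** The best case for acting is this. The Protocol itself fixes both the entry floors and a reduction-from-Baseline rule, so their interaction is not purely an SAP matter. Its language of a meaningful difference, and the parallel EHP-30 threshold described as a score change (Section 9.3.2), point to absolute units. Low means are realistic: in the phase 2 study (Section 2.2.4.2), group mean Baseline pelvic pain was 14.6-15.6 mm on a 100 mm scale, or about 1.5 out of 10. The power margin is thin: f = 2% with a 35% control rate already gives about 94.5%, and f = 5% on both endpoints gives joint power of 0.942² = 88.7% or 0.934² = 87.2%. The remedy would be cheap: accept a drop of at least the smaller of T and Baseline.

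What stands is the arithmetic and the absence of any stated link between T and the floors. The rest is weaker.
- Absolute units are a natural reading, not a stated one.
- The phase 2 figures come from another instrument and other entry rules. They also cut the other way: the mean change there on 40 mg was −10.4 mm, about 1 point in 10, so data with low means can also yield a low threshold.
- The planning rates are for whole groups, with the control rate placed within the range of similar phase 3 trials. Low-Baseline non-response may already be inside them; applying the 20 points only to the rest replaces the plan's assumption and does not refute it.
- An 8b-only admission affects NMPP alone. A low menstrual mean affects dysmenorrhea alone.
- The remedy would count drops smaller than the anchor-derived meaningful change as response. For a woman starting below T it would also require every score in the final window to be 0, so a single day scored 1 would fail her. The gain is uncertain and the endpoint's meaning changes.

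**Conclusion.** No change to the plan follows. The interaction between entry floor and threshold is real as a possibility: Baseline means of 1.25 or lower for NMPP, and roughly 1.1 to 1.6 for dysmenorrhea with five to seven menses days, are admissible, and an absolute threshold above them could not be met. Whether it arises depends on the unit and size of two thresholds that the Protocol leaves to the SAP, where the handling of a low Baseline also ordinarily belongs. Because the thresholds are anchored on this trial's own patients, analysts deriving them will see the Baseline distribution before choosing.

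The consequence would be limited. Affected women would be non-responders in all arms, so there is no bias between groups and no inflation of type I error. The cost is some power: under 2 points per endpoint at f = 5%, and about 9 to 10 points at f = 20%, if the 20-point effect applies only to the remaining women. These figures are illustrative and do not show that the stated 95% is wrong. Keeping one meaningful-change standard for everyone, at the price of some insensitivity in women with low means, is a fair trade-off.
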